## **OBJECTIVES**

### **PRIMARY**

Investigate the effect of daily ingestion of fermented milk containing 40 billion LcS on the changes in the concentration of salivary IgA in amateur triathletes participating in this study, before and after an official triathlon competition.

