## Population and design of the study

In order to perform this research project, it is proposed to recruit and select 70-80 amateur triathletes, between 25 to 45 years, both sexes, residing in the city of São Paulo, Brazil, who will be participating in the same triathlon competition.

Regarding the sample size, it was determined using G\*Power software (version 3.1.9.6). The analysis was conducted using the F tests - ANOVA: repeated measures, within-between interaction option to accommodate the mixed design of the study, which includes two groups and five repeated measurements. It is important to mention that to carry out the sample size calculation alignment with the study's primary objective, which is associated with the salivary IgA, we used the data presented in the study performed by [name] et al., 2019. In agreement with this data, the following parameters were used to calculate the required sample size: Effect size (f): 0.15 ([name] et al., 2019). Alpha error probability ( $\alpha$ ): 0.05. Power (1- $\beta$  error probability): 0.85. Correlation among repeated measures: 0.5. Nonsphericity correction ( $\varepsilon$ ): 1. Based on these inputs, the total sample size required to achieve the desired power of 0.85 is 62 participants. Thus, 70-80 athletes will be included in this study. This sample size will be distributed equally between the two groups (35-40 participants per group).

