## **Cardiopulmonary Test**

The physical capacity of each volunteer will be characterized through a cardiopulmonary test that will be performed on a treadmill attached to the gas analyzer, with electrocardiography and gas analysis software. This test will be performed at the Research and Training Olympic Center, an institution belonging to the Municipal Secretariat of Sports, Leisure, and Recreation of the City of São Paulo.

In order to carry out the cardiopulmonary test, the patient's preparation rules will be followed, which include hair removal from the place where the electrodes will be placed, cleaning the skin with alcohol, and scarification with water sandpaper number 400. The placement of the electrodes will follow the described by Salient (2019) for the formation of the 12 leads in the Einthoven triangle.

The cardiopulmonary test will be performed with a ramp protocol, with a fixed incline of 1% and load increment (1km/h) every minute until the maximum speed of the treadmill, at which time the increment of 2% incline begins every minute. The protocol should be started

with 10.9 or 8 km/h according to the time for a 10 km race, with the time below 35', between 35' and 46', and above 46', respectively. Tests should be maximum, being interrupted by limiting symptoms / intense physical fatigue.

The data obtained in this test in conjunction with body composition will be used to stratify the volunteers into four different strata. In addition, the randomization of volunteers in each strata will follow the process: firstly, the researcher [name], will be responsible for creating a computer-generated random list of numbers for the treatment groups of either LcS or placebo, and after each volunteer will be anonymously and sequentially allocated in these groups according to their recruitment ordering number in the program.

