### **LcS ingestion**

After stratification, the volunteers will be separated into two groups: (1) LcS Group (LcSG), which will ingest 1 bottle of fermented milk (80 grams) with  $40 \times 10^9$  of LcS per day; and (2) placebo/unfermented milk Group (PLG), which will consume 1 bottle of unfermented milk (80 grams), due to the absence of LcS. Both groups will begin the ingestion 30 days before the competition, maintaining it until 14 days after the competition. As previously mentioned, all volunteers will be oriented to stop drinking immediately and seek medical attention if any symptoms of gastrointestinal disturbance are perceived. To ensure the development of a double-blind study, all bottles used in the study will be kindly provided by YAKULT S/A Industria e Comércio, Brazil. The bottles will be named A and B by the company and will have the same taste, appearance, and smell. Information on the presence or absence of LcS in the bottles will be accessed only after all analyzes have been performed. In addition, to monitor the adherence of volunteers to the study's protocol, we intend not only to request the return flask fortnightly (empty or not) but also to maintain routine contact via social media with the volunteers. This contact also will allow us to provide responses and orientations to any questions by them, as well as, weekly, to perform auditing concerning the study's conduction.

It is important to clarify that the Yakult S/A Industria e Comércio, Brazil, will provide the fermented milk containing LcS and also the placebo/unfermented milk. In addition, Yakult Honsha Co., Ltd. Japan, will fund the development of the study, which includes all the materials needed to perform the collection, procedures, storage, and laboratory evaluations of

the biological samples obtained on all occasions described in the study. Besides, it is noteworthy to mention that the design, management, data check and analysis, and preparation of the reports/articles of the study are entirely under the responsibility of the researchers.

Regarding the ingestion period, it is based on the study by [name] et al. (2019), which showed a remarkable capacity of fermented milk containing LcS in modulating several immune/inflammatory parameters, both systemic and in the upper airways, in runners after a marathon.

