### **Statistical analysis**

All data obtained during the development of this study will be added to a unique file, preferentially in an Excel file, which will be available to all researchers not only to consult and check the data quality/accuracy but also to add any results through GOOGLE-DRIVE. It is noteworthy to clarify that, to perform all the statistical analysis proposed here, we will follow the "intention-to-treat" (ITT) analysis, not only because it is recommended as an analysis strategy for randomized studies but also to be possible to maintain the sample size, as well as to use the data obtained from the participants regardless of whether they complete the study since ITT considers all randomized participants in the analysis, whether they drop out or not. In addition, the multiple imputation (MI) method will be applied to handle missing data since

MI fills in missing values by generating plausible numbers derived from distributions of and relationships among observed variables in the data set. Beyond these analyses, in order to check and increase the reliability of the results obtained in the ITT analysis, we also intend to conduct the statistical analysis regarding the per-protocol (PP) analysis, which will be used exclusively the complete data obtained from the volunteers.

After all data will be added to the Excel file and the data quality/accuracy is checked by the researchers, these data will be initially compared with the Gaussian curve, and normality determined for each variable.

If the variable presents a parametric behavior, the mean and standard deviation will be used, and they will be compared by using the ANOVA test for repeated measures with post hoc tests for intragroup (longitudinal) and intergroup (cross-sectional) analysis.

On the other hand, if the data present a non-parametric behavior, they will be represented by median and interquartile ranges, and they will be compared by using Friedman's test with Müller-Dun post hoc test for intragroup (longitudinal) and the Kruskal-Wallis test with Müller Dunn's post hoc test for intergroup (cross-sectional).

Using Pearson (for parametric values) or Spearman tests (for non-parametric values), the correlation between the variables studied will be evaluated.

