In addition, the McNemar Chi-square test (with Yates correction) will be used to determine whether the difference in the number of volunteers who presented or not upper airway symptoms, as well as in the duration of the symptoms, is significantly different in each group (paired analysis). Additionally, Chi-square test will be used to perform the same analysis but between the volunteer groups (unpaired analysis).

A risk of less than to 0.05 ( $p<0.05$ ) will be considered statistically significant for every study.

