**Recommendations:**

RECOMMENDATION 1- It is the researcher's obligation to develop the research project in full compliance with the proposal submitted to the CEP. Changes and alterations to the protocol must be communicated in the form of an AMENDMENT through Plataforma Brasil.

Address:	[name]		
Neighborhood:	VILA CLEMENTINO	ZIP CODE:	04.021-
UF: SP	Municipalit	SAO PAULO	
Phone:	y:		E-mail [contact]

Continuation of Opinion: 7.349.261

**RECOMMENDATION 2-** From the date of approval, it will be necessary to send partial reports (every six months) and the final report (at the end of the study), by means of a NOTIFICATION on the Brazil Platform. Researchers must inform and justify to the CEP any need for temporary suspension or permanent suspension of the research. Incidents and adverse events must also be reported to CEP-Unifesp by means of a NOTIFICATION on the Brazil Platform.

**RECOMMENDATION 3-** Researchers should take all necessary precautions when collecting and storing data in order to guarantee the secrecy and confidentiality of the research participants' information. It is recommended to download the data collected to a local electronic device, deleting any data from virtual platforms or the cloud. The research protocol documents (files of forms, terms, data and samples) must be kept for at least 5 years after the end of the research.

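### Salivary IgA has no single prespecified group-by-time test: a normality check picks the method, and the non-parametric branch cannot test the interaction the trial was sized for

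*Combined protocol and SAP*

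**What the plan says.** Under Objectives, Primary, the aim is the effect of the LcS milk "on the changes in the concentration of salivary IgA in amateur triathletes participating in this study", before and after the race. Under Population and design of the study, the sample size comes from the G*Power option for "repeated measures, within-between interaction option to accommodate the mixed design of the study": two groups, five measurements, 62 participants required and 70 to 80 planned.

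The Statistical analysis section names no primary test for IgA. It says that "these data will be initially compared with the Gaussian curve, and normality determined for each variable", without giving a normality test, a threshold or a transformation. A variable judged parametric goes to repeated-measures ANOVA, with post hoc tests within and between groups. A variable judged non-parametric goes to Friedman's test with a Dunn-type "post hoc test for intragroup (longitudinal) and the Kruskal-Wallis test with" a further Dunn-type post hoc test for the cross-sectional comparison between groups. On error control there is only a general threshold: p below 0.05 "will be considered statistically significant for every study".

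**The concern.** The primary question is whether the arms change differently over the five occasions. In the non-parametric branch nothing tests that. Friedman's test asks whether one arm changes over time. Kruskal-Wallis asks whether the arms differ at one occasion, and it ignores baseline. In the parametric branch the ANOVA would normally produce the interaction term, but the plan does not make it the deciding result.

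If IgA is judged non-normal, a claim of benefit could therefore rest on whichever occasion reaches p < 0.05, or on a change within the LcS arm alone. Neither keeps the error rate for the primary question at 5%.

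**Working it through.** **1. The plan's own figure.** Inputs from Population and design of the study: f = 0.15, alpha = 0.05, rho = 0.5, epsilon = 1, k = 2 groups, m = 5 occasions.

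lambda = f² · N · m · epsilon / (1 − rho); df1 = (k − 1)(m − 1)epsilon = 4; df2 = (N − k)(m − 1)epsilon.

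- N = 62: lambda = 0.0225 × 62 × 5 / 0.5 = 13.95; F(4, 240); power 0.857. N = 60 gives 0.844, so 62 is the smallest even N reaching 0.85.
- N = 70: lambda = 15.75; power 0.902.
- N = 80: lambda = 18.00; power 0.940.

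The 62 reproduces exactly. It belongs to the interaction test and to no other test in the plan.

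**2. What each planned test addresses.**

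| Branch | Test | Compares arms? | Compares change over time between arms? |
|---|---|---|---|
| Parametric | Repeated-measures ANOVA | Yes | Yes, but not named as decisive |
| Non-parametric | Friedman, per arm | No | No |
| Non-parametric | Kruskal-Wallis, per occasion | Yes | No |

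**3. False positives if each occasion is tested at 0.05.** Simulated with no treatment effect, 20,000 trials per setting. The data are multivariate normal, but these rank tests give the same result on exponentiated data. The correlations 0.3 and 0.7 are assumptions around the plan's 0.5.

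| | rho 0.3 | rho 0.5 | rho 0.7 |
|---|---|---|---|
| Any of 4 post-baseline, 35 per arm | 17.6% | 15.7% | 13.5% |
| Any of 4 post-baseline, 40 per arm | 17.5% | 15.7% | 13.3% |
| Any of 5, 35 per arm | 21.1% | 18.6% | 15.5% |
| Any of 5, 40 per arm | 20.9% | 18.4% | 15.2% |
| Bonferroni over 4, 35 per arm | 4.6% | 4.1% | 3.6% |

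For independent tests the figures would be 1 − 0.95⁴ = 18.5% and 1 − 0.95⁵ = 22.6%. A single designated occasion holds about 5%.

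**4. Power if the planned effect is real.** f = 0.15, 35 per arm, rho 0.5, 20,000 trials. An effect at one occasion only corresponds to a difference of 0.75 SD: the centred half-differences are 0.30 once and −0.075 four times, and (0.09 + 4 × 0.005625)/5 = 0.0225 = 0.15².

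| Where the effect lies | Interaction F | Bonferroni/Holm Kruskal-Wallis, any of 4 |
|---|---|---|
| Immediately post-race only (0.75 SD) | 0.903 | 0.701 |
| Immediately post-race, half of it at 72 h | 0.903 | 0.709 |
| 24 h pre-race and immediately post-race (0.61 SD) | 0.904 | 0.654 |
| All four post-baseline occasions (0.75 SD) | 0.900 | 0.928 |

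Adjusting Kruskal-Wallis for multiplicity therefore does not replace the interaction test unless the effect is sustained.

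**5. If the two Friedman results were contrasted.** No treatment effect, 35 per arm, rho 0.5, 10,000 trials. Both arms share a shift of d SD immediately post-race and d/2 at 72 h (assumed).

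| d | 0 | 0.1 | 0.2 | 0.3 | 0.4 | 0.5 | 0.6 | 0.8 |
|---|---|---|---|---|---|---|---|---|
| Exactly one arm significant | 9% | 13% | 26% | 44% | 50% | 37% | 18% | 1% |

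About half of these favour LcS.

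**6. Chance of entering the non-parametric branch.** The documents give no IgA distribution. Assuming log-normal IgA and a Shapiro-Wilk test on 70 values, rejection occurs in 14% of runs at log-SD 0.1, 42% at 0.2, 74% at 0.3, 91% at 0.4 and at least 98% at 0.5 or more.

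**The case against.** - **The gap affects one branch only.** Read with the sample size section, the ANOVA branch supplies the interaction, and the chance of leaving that branch is unknown. This is true and limits the reach of the point. But the primary analysis should not depend on a pre-test whose rule is unstated.
- **Kruskal-Wallis after randomisation is a valid comparison of arms.** At one designated occasion it is, and it holds 5%. None is designated.
- **A Dunn post hoc test is planned.** With two arms it adds nothing at an occasion and does not adjust across occasions. If men and women were compared as further groups, the interaction with time would still be untested.
- **Blinding protects against selection.** Bottle identity "will be accessed only after all analyzes have been performed", so the branch cannot knowingly be chosen to favour LcS. That stands, but blinding neither supplies the missing test nor controls error across occasions.
- **The largest figures are conditional.** The plan does not say the Friedman results will be contrasted, and that rate runs from 1% to 50% with the assumed race effect. The 16% counts both directions; at least one result favouring LcS occurs in 7.9% of null trials, against 2.5% for one test. These figures show possible size. The defect itself is read from the text.
- **A four-degree-of-freedom test also designates no occasion or direction.** This is fair. One prespecified baseline-adjusted contrast would also close the gap, but the 62 was not calculated for it. The interaction test matches the existing calculation, and estimates by occasion supply the direction.

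**Conclusion.** The point holds and must be fixed before unblinding. The sample size is correct for the interaction, but if IgA is judged non-normal the plan contains no test of it, no designated occasion and no error control across occasions. That conclusion follows from the text alone.

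Its size depends on assumptions. The roughly 16% false-positive rate assumes every post-baseline occasion is tested at 0.05, with correlation 0.5. The loss of about 0.2 in power under multiplicity adjustment assumes f = 0.15, N = 70 and an effect confined to one or two occasions; for a sustained effect there is no loss. How often the branch would be entered cannot be settled from the documents.

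**What to change.** In the Statistical analysis section, prespecify one primary analysis of salivary IgA with no normality pre-test:

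- Model log IgA at all five occasions in a linear mixed model with arm, occasion, arm-by-occasion and the randomisation strata (under Cardiopulmonary Test, the test and body composition data "will be used to stratify the volunteers into four different strata"). Use unstructured covariance and Kenward-Roger degrees of freedom.
- Make the arm-by-occasion test the single primary test at 0.05.
- In all cases report the between-arm ratio of change from baseline, with 95% CI, at each post-baseline occasion. Limit significance claims for these to Holm-adjusted tests after a significant primary test.
- If multiple imputation is kept, fit this same model in each imputed data set and pool.
- As a prespecified sensitivity analysis, give a permutation test of the same interaction, with arm labels permuted within strata. It is not a data-driven replacement.
- State that within-arm tests are descriptive and are not evidence of a treatment effect.

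**Cost.** No new samples or visits. It changes the protocol, and the ethics committee's Recommendations state: "Changes and alterations to the protocol must be communicated in the form of an AMENDMENT". Results become ratios of geometric means, and f = 0.15 is then assumed to apply on the log scale.

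Unstructured covariance costs a little power if sphericity holds. With complete data, the same lambda and F(4, N − 5), power is 0.832 at N = 62 (instead of 0.857), 0.883 at 70 (instead of 0.902) and 0.927 at 80 (instead of 0.940). N = 64 gives 0.846 and N = 66 gives 0.859, so about 66 analysable participants are needed for 0.85. That is within 70 to 80 but leaves room for only four losses at 70. If 10% were unusable (an assumption), 63 would remain and power would be 0.839; from 80, 72 would remain. Recruiting towards 80 is therefore safer.

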## WORK PLAN AND SCHEDULE

For the performance of the present study, we propose a work plan and schedule that will need 12 months to be developed. Thus, a scale of monitoring and collection of materials will be recommended, which initially will depend on the availability of each volunteer recruited to carry out the long-term triathlon competition.

Thus, we propose the following work plan and schedule:

- Recruitment of athletes and performance of clinical evaluations on all volunteers included in the study;
- Collection of blood, saliva, and nasal swab samples before starting the daily intake of fermented milk containing or not the bacteria (LcS group, n=35-40; Placebo group, n=35-40, respectively).

- study volunteers will ingest the fermented milk for 44 days;
- Collection of blood, saliva, and nasal swab samples 24 hours before the competition;
- realization of the competition by all volunteers included in the study;
- Collection of blood, saliva, and nasal swab samples immediately after the end of the competition;
- Collection of blood, saliva, and nasal swab samples 72 hours after the competition;
- Collection of blood, saliva, and nasal swab samples 14 days after the competition;
- Evaluation of the occurrence of upper airway symptoms throughout the study's period;
- Performing the laboratory evaluations described in the Material and Methods section; - Statistical analysis of the results and preparation of the report.

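### The Yates-corrected McNemar test planned within each arm runs at about 2% rather than 5% with 35-40 athletes; a mid-p version would recover a conditional amount of power for this secondary before-after analysis

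*Combined protocol and SAP*

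**What the plan says.** The Statistical analysis section states that "the McNemar Chi-square test (with Yates correction) will be used to determine whether the difference in the number of volunteers" with or without upper airway symptoms, and also the duration of symptoms, "is significantly different in each group (paired analysis"). For the comparison of LcS with placebo, a separate "Chi-square test will be used to perform the same analysis but between the volunteer groups (unpaired analysis"). The Yates correction is attached only to the McNemar test. A p-value below 0.05 "will be considered statistically significant for every study".

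Under Population and design of the study, "This sample size will be distributed equally between the two groups (35-40 participants per group"). The Work plan repeats the figure: "LcS group, n=35-40; Placebo group, n=35-40".

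The protocol's Objectives section makes incidence and duration of upper airway symptoms secondary. The primary objective is salivary IgA, and the sample size was set on it. No discordance rate, expected within-arm change, size or power is given for the McNemar test. The section also does not say which two occasions are paired.

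**The concern.** McNemar's test uses only the discordant pairs, that is, athletes whose symptom status changes between the two occasions. With 35-40 athletes and 20-50% discordance, that is about 7 to 20 pairs (0.20 × 35 = 7; 0.50 × 40 = 20). With counts this small, subtracting 1 from the difference in the Yates statistic often moves the rejection boundary by a whole athlete. The test then rejects much less often than its nominal 5%.

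At stake is the ability to detect a real before-after change in symptoms within an arm. The result would be presented as a 5% test when it ran at about half that level or less. The sample size was not set for this outcome, so there is no planned reserve of power to absorb the loss.

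**Working it through.** **1. The plan's own figure.** The only sample-size figure is 62 in total, for salivary IgA. The method was described as follows: "The analysis was conducted using the F tests - ANOVA: repeated measures, within-between interaction option", with "Effect size (f): 0.15", correlation 0.5, ε = 1, two groups, five measurements, α = 0.05 and power 0.85.

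- λ = f²·N·m·ε/(1−ρ) = 0.0225 × 62 × 5 × 1/0.5 = 13.95
- df1 = (2−1)(5−1) = 4; df2 = (62−2)(5−1) = 240
- The noncentral F gives power 0.857 at N = 62 and 0.844 at N = 60.

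So 62 reproduces. It says nothing about the McNemar test.

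**2. Inputs for the McNemar check.** From the plan: n = 35 and n = 40 complete pairs per arm, threshold 0.05, Yates correction. Assumed, because the documents do not give them: the proportions who gain symptoms (p₁₀) and lose them (p₀₁).

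**3. Formulas.** Let b and c be the numbers gaining and losing symptoms, and D = b + c. Then D ~ Binomial(n, p₁₀ + p₀₁) and b given D ~ Binomial(D, p₁₀/(p₁₀ + p₀₁)). Rejection rules:

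- Yates: (|b−c|−1)²/D > 3.841
- Uncorrected: (b−c)²/D > 3.841
- Mid-p: 2·P(X < k) + P(X = k) < 0.05, where k = min(b, c) and X ~ Binomial(D, ½)

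Size and power are the sums of the probabilities of all rejecting (b, c).

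**4. How the correction acts, at D = 8.** For a 7–1 split, Yates gives (6−1)²/8 = 3.125, which does not reject. Mid-p gives 2 × 1/256 + 8/256 = 10/256 = 0.039, which rejects. Under no change, Yates rejects only an 8–0 split, with probability 2/256 = 0.8%. Mid-p also rejects 7–1, giving 18/256 = 7.0%. At D = 9 or 10 the two tests make identical decisions. The overall size averages over D.

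**5. True size under no change (%), by discordance rate.**

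| Discordant | Yates, n=35 / 40 | Mid-p, n=35 / 40 | Uncorrected, n=35 / 40 |
|---|---|---|---|
| 10% | 0.3 / 0.5 | 1.3 / 1.7 | 3.8 / 4.3 |
| 20% | 1.6 / 1.9 | 3.6 / 3.8 | 4.6 / 4.4 |
| 30% | 2.3 / 2.3 | 4.2 / 4.3 | 4.3 / 4.4 |
| 40% | 2.4 / 2.4 | 4.6 / 4.7 | 4.6 / 4.9 |
| 50% | 2.5 / 2.7 | 4.7 / 4.6 | 5.1 / 5.3 |
| 80% | 3.0 / 3.1 | 4.4 / 4.5 | 5.3 / 5.1 |

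From 10% to 80% discordance, Yates never exceeds about 3.1% and mid-p never reaches 5%. The uncorrected test can slightly exceed 5% (maximum 5.4%). The exact conditional test runs at 1.6-3.0% over 20-50% discordance, close to Yates.

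**6. Power under assumed change, Yates v mid-p.**

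| Gain / lose | n=35 | n=40 | Gain in points |
|---|---|---|---|
| 25% / 5% | 0.488 v 0.594 | 0.562 v 0.662 | 10-11 |
| 30% / 10% | 0.357 v 0.464 | 0.413 v 0.525 | 11 |
| 30% / 2% | 0.864 v 0.917 | 0.916 v 0.951 | 3-5 |
| 20% / 0% | 0.728 v 0.857 | 0.839 v 0.924 | 8-13 |
| 30% / 0% | 0.973 v 0.991 | 0.991 v 0.997 | 1-2 |

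**7. Using the one rate in the protocol.** Population and design of the study cites an illness incidence of about 30% in triathletes. This is a marginal rate, not a discordance rate. If 30% have symptoms after the race, independently of status before it, the gain from mid-p is 7-8 points with 5% symptomatic before, 10-11 with 10%, and 8-10 with 15%. Over a wider grid under independence (0-30% before, 10-50% after), the gain over Yates ranged from 0 to 19 points.

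**The case against.** The plan accepts a risk below 0.05, and a test running at about 2% keeps to that. Yates also behaves much like the exact conditional test (power 0.488 v 0.490 at n=35 for 25%/5%), which many statisticians choose because its level is guaranteed. That stands as far as validity goes: the planned test is conservative, not wrong. It is a weak reason to keep Yates here, because averaged over the number of discordant pairs mid-p also stayed below 5% at every rate tried. Mid-p can exceed 5% for a particular D, as at D = 8 above, so someone who wants the level held for every D would still prefer Yates or the exact test.

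A reader might infer that the correction costs this trial about 10 points of power. The documents do not support a single figure. They give no discordance rate, and the anamnesis screens out upper airway symptoms from pre-existing conditions, which may leave few athletes symptomatic at the start. If none are and 30% are after the race, only 1-2 points are lost.

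A reader might also infer that the test of LcS against placebo is weakened, or that its chi-square needs the same change. Neither follows. McNemar is planned only within each arm, where the race and the passage of time are confounded with the product. The between-group chi-square carries no Yates correction as written.

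Nor does the correction by itself make a non-significant arm uninformative. In the first two scenarios mid-p power is still only 0.46-0.66, so the number of athletes is the main limit.

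**Conclusion.** The point holds as a minor improvement. With 35-40 complete pairs, the planned test has a true size of about 1.6-2.7% at 20-50% discordance, and lower with fewer discordant pairs. Mid-p has about 3.6-4.7% over the same range. The size result does not depend on which two occasions are paired, only on how many athletes change status.

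The power gain rests entirely on assumed proportions gaining and losing symptoms: 10-11 points for 25%/5% and 30%/10%, 3-5 points for 30%/2%, and 1-2 points for 30%/0%. It should be quoted with those conditions.

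The consequence is confined to a within-arm analysis of an outcome that the protocol's Objectives rank as secondary. It does not touch the primary salivary IgA analysis or the randomised comparison of symptoms.

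**What to change.** In the Statistical analysis section, replace the Yates-corrected McNemar chi-square with the mid-p McNemar test, and limit it to paired occurrence (yes/no) of upper airway symptoms within each arm. The limit is needed because the same sentence also applies McNemar to symptom duration, which is not a paired yes/no outcome; changing the version of the test does not settle that.

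The change takes a few words and needs no new data, visits or participants. Its price is that the false-positive rate of each within-arm test rises from about 2% to just under 5%. That is still within the stated limit, although the Statistical analysis section describes no multiplicity adjustment for these within-arm symptom tests. This point requires no change to the between-group chi-square.
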